4.4 Interim Analyses and Data Monitoring

The trial data is reviewed periodically by an independent Data Monitoring Committee (DMC). The DMC reviews certain safety and efficacy data sets as defined in the charter and provides written reports to the sponsor.

The 6 month data for PTPs was analyzed for regulatory purposes as a final analysis for Part A of the study. That analysis for PTPs is an interim analysis as defined in the protocol because the trial is ongoing for Part B and the extension phase. Safety was assessed in 20 PTPs before enrollment of PUPs began.

This SAP describes the interim analysis of part B of the study, originally planned for 25 PUPs. Amendment 3,6 and 7 of the protocol added up to 25 additional subjects to part B and the study was opened for MTPs. It will summarize data from Part B without extension phase. Extension study data will be described in the final CSR.

4.5 Data Rules

All bleed and infusion data will be entered into the EPD (hospital infusions will be entered into the eCRF) and imported into SAS. If an infusion is given for a bleed and the bleed information is not provided, the infusion date and time will be used as the bleed date. Vice versa will a bleed date be used for surrogate of a missing infusion.

All bleeds include spontaneous bleeds, trauma, untreated bleeds and 'other' bleeds. 'Other' bleeds are infusions with reason given as 'other', an untreated bleed is a bleed with no corresponding infusion for the bleed.

During the period of ITI treatment all prophylactic infusions will also be counted as ITI treatment, as during ITI no other prophylaxis will be given.

4.5.1 Baseline values

Baseline values for vital sign measures and laboratory values are planned to be taken at Visit 2 before administration of study drug. If these values are not available, values taken before first administration of study drug will be considered (e.g., values taken on Visit 1). In case of more than one available value before first administration of study drug, the non-missing value closest to Visit 2 will be taken.

4.5.2 Annualized bleed rate

The definition of annualized bleed rate is generally defined as

```
(#of bleeds in period) * 365.25/(last datetime of period- first datetime in period)
```

```
60 \cdot 60 \cdot 24
```

The different periods used for analysis are described in section 6.2.1.

4.5.3 24 hours rule

Count no more than 1 bleed in a calendar day. If there is more than 1 bleed in a calendar day, to determine the bleed that gets counted, give priority to treated bleeds, spontaneous or trauma bleeds, then joint bleeds. Otherwise, count the first bleed in the day. Severity and treatment response will come from this selected bleed. Bleed site will be aggregated over all bleeds from that day. Regardless of which bleed is selected, the time of the first bleed in the day will be used. All other infusions in the day for treating bleeds will be considered follow-up infusions.

4.5.4 72 hours rule

Do not count a spontaneous joint/muscle bleed if it occurs within 72 hours of a bleed (or infusion for that bleed) at the same site. For a bleed to be affected by this rule, all sites listed on the bleed must also be specified in the previous bleed. If the current and previous bleeds are both skin/mucosa bleeds, this rule does not apply. Such infusions for bleeds will be considered to be follow-up infusions.

Joint bleeds can occur in more than 1 joint site. For each joint bleed, count all sites (combining left and right). For the table showing the Joint Site frequency, sum counts over all sites.

4.6 Blind Review

The results of the final data assessment will be documented in the final list of important deviations, validity findings and assignment to analysis set(s). Any changes to the statistical analysis prompted by the results of this review or other reasons of study data will be documented in an amendment and, if applicable, in a supplement to this SAP.

4.7 Recovery

Recovery or incremental recovery

The terms recovery and incremental recovery are synonymous and are used interchangeably in this context. Recovery is calculated using the formula below:

Recovery=(post-infusion FVIII value – pre-infusion FVIII value) * body weight / dose (in IU)

Recovery will be determined by collecting a sample for the FVIII level pre-infusion of FVIII and a second sample collected 20 to 30 minutes post-infusion of FVIII. The exact sampling times before and after infusion and the dose administered will be documented in the CRF.

If a FVIII concentration value is below the LLOQ (lower limit of quantification), a data point will be substituted by one half of this limit.

A validity flag for recovery values and their corresponding pre- and post-infusion FVIII values will be created. These FVIII values and their corresponding recoveries will be considered valid except when any of the following conditions apply:

- If pre-infusion FVIII ≥ post-infusion FVIII [biologically impossible in the absence of inhibitors]
- If pre-infusion FVIII > 40 IU/dl (note 1 IU/dl=1%) [protocol violation]

• If post-infusion FVIII < 10 IU/dl (note 1 IU/dl=1%) [biologically impossible in the absence of inhibitors]

Furthermore, if there are multiple FVIII values for a subject and timepoint, only the record with the highest FVIII will be used. The others values will be excluded from the analysis dataset.

Measurements of pediatric patients' weights are performed at each visit. When calculating recovery, the available body weight measurement from the same or most recent visit will be used. If this value is missing, then the body weight from the next visit will be used.

As measurements of recovery values are expected not to be often taken in this very young population, they will only be listed.

5. Analysis Sets

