This SAP describes the objective, study design, analysis sets, all endpoints, and statistical analysis methods for the interim analysis of the part B of study 13400, where Previously Untreated Patients (PUPs) and Minimally Treated Patients (MTPS) where treated. Planned end was 50 exposure days (EDs), in case of inhibitor development the subjects should leave the study and get treatment in the extension part or outside of the study. Complete details of Tables, Listing and Figures (TLFs) specifications as well as dataset details and data handling

specifications will be provided in "TLF specifications" and "Analysis Datasets" documents which are an integral part of this SAP.

The analysis of the 6-month data for Previously Treated Patients (PTPs) in Part A is complete and reported in the clinical study report A51496. This SAP is applicable to completion of Part B. The extension study is ongoing.

The data upon completion of Part B will be analyzed later. The overall study will be closed after all subjects in Parts A and B have completed their respective extensions, in accordance with the protocol definition of 'end of study' (that is, last visit of the last subject [including subjects in the extension study]).

Further details can be found in the Clinical study protocol, which contains comprehensive information on the study drug.

2. Study Objectives

General objectives of this study are:

Primary objective

• To demonstrate the safety and efficacy of treatment with BAY 81-8973 for prophylaxis and breakthrough bleeds in children with severe hemophilia A

Secondary objectives

- To assess the safety and efficacy of BAY 81-8973 during surgeries
- To assess incremental recovery of BAY 81-8973
- To characterize pharmacokinetics in a subset of children

As during part B of this study, where PUPs and MTPs were treated up to 50 EDs (or development of inhibitor) only few recovery and pharmacokinetic data were collected, the last two secondary objectives will be analyzed in the final analyses of the study where more data are available.

3. Study Design

From the protocol:

This is a phase-III multicenter, open-label uncontrolled study to demonstrate safety and efficacy of treatment with BAY 81-8973 for prophylaxis, breakthrough bleeds, and surgeries in children with severe hemophilia A. The study will be conducted worldwide.

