6.2.1 Additional analyses

For subjects undergoing surgery (both major and minor), the following information will be listed:

- Blood loss
- Need for additional hemostatic medication, including blood products
- Units of blood transfused
- Hemostatic-related surgical complications
- Assessment of hemostasis as excellent, good, moderate or poor
- Study drug usage

Factor VIII concentration values and recovery values will be listed where available. As only few values are expected, no tabulation will be done.

Health care resource utilization will be tabulated. This includes additional visits to hematologists, family physician, nurse or other health care provider, additional tests, like blood tests but also radiological tests, hospital visits and nights in hospital.

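### SAP v2.0 section 4.7 can label genuine inhibitor-affected Part B recoveries as not valid, and SAP v2.0 and its Supplement disagree on whether recovery is summarised

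*SAP*

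**What the plan says.** SAP v2.0 section 4.7 defines recovery as (post-infusion FVIII − pre-infusion FVIII) × body weight / dose. It creates a validity flag with three conditions, any one of which makes a recovery not valid. Two are at issue:

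- "If pre-infusion FVIII ≥ post-infusion FVIII [biologically impossible in the absence of inhibitors"
- "If post-infusion FVIII < 10 IU/dl (note 1 IU/dl=1%) [biologically impossible in the absence of inhibitors"

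The third, a pre-infusion level above 40 IU/dl, is justified as a protocol violation and is not questioned here. For a concentration below the lower limit of quantification (LLOQ), "a data point will be substituted by one half of this limit".

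On presentation, section 4.7 says: "As measurements of recovery values are expected not to be often taken in this very young population, they will only be listed". Section 6.2.1 agrees: "As only few values are expected, no tabulation will be done". Section 2 explains that "only few recovery and pharmacokinetic data were collected" in Part B and that "the last two secondary objectives will be analyzed in the final analyses of the study".

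Supplement 1.0, dated six days after SAP v2.0, names recovery as a secondary parameter in section 2.1. It has recovery calculated by section 4.7 and summarised, with a subject listing as a further item. Its introduction says that it changes no analysis.

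The Part A SAP (version 2.1, section 6.2) has the pre ≥ post rule and the pre > 40 rule, but no 10 IU/dl rule. It leaves flagged values out of the descriptive tables. SAP v2.0 contains no such statement.

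**The concern.** Both rules state their own limit: they identify an impossible value only if no inhibitor is present. Neither is conditioned on that, and nothing else in SAP v2.0 or the Supplement adds the condition.

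Part A enrolled children without a current inhibitor and, with one narrow exception, without an inhibitor history, so the reasoning broadly fitted there. Part B enrols previously untreated and minimally treated children, in whom inhibitor development is the main safety question. The protocol asks for a recovery with the confirmatory inhibitor test (sections 7.3.2.1 and 7.5.3.4), requires pre- and post-infusion samples for confirmation (section 14.5), and makes decreased recovery part of the definition of a clinically relevant inhibitor (section 6.1.5). A near-zero recovery in such a child is a finding, not an error.

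At stake is the credibility of a descriptive secondary parameter. A summary that omits these values would describe recovery as if inhibitors had not reduced it.

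**Working it through.** There is no stated figure to reproduce. The check has three parts.

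**1. Complete loss of recovery.** If both samples are below the LLOQ, section 4.7 sets pre = post = LLOQ/2. Then pre ≥ post is true, and the recovery is flagged at any dose and for any LLOQ.

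**2. Where the 10 IU/dl cut falls.** Inputs:

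- Protocol section 6.4: 50 IU/kg is expected to bring FVIII to about 80–100%. Expected recovery = 80/50 to 100/50 = 1.6 to 2.0 IU/dl per IU/kg.
- Protocol sections 6.1.1 and 6.4: Part B prophylaxis is 15–50 IU/kg.
- Protocol section 6.1.5: normal recovery is more than 66% of predicted.
- Assumptions: the rise is proportional to dose, and predicted recovery is 1.6–2.0. The pre-infusion level is near 0, with 5 IU/dl as a sensitivity value.

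Expected rise = dose × (1.6 to 2.0). Cut as a share of the expected rise = (10 − pre) / expected rise.

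| Dose (IU/kg) | Expected rise (IU/dl) | 66% of expected rise | Cut, pre near 0 | Cut, pre 5 |
|---|---|---|---|---|
| 15 | 24–30 | 15.8–19.8 | 33–42% | 17–21% |
| 25 | 40–50 | 26.4–33.0 | 20–25% | 10–12.5% |
| 50 | 80–100 | 52.8–66.0 | 10–12.5% | 5–6% |

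Every cut lies below 66%. The rule therefore removes values from the low end of the range that the protocol itself calls reduced, and it reaches furthest at the lowest dose.

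**3. Effect on a summary, if one is produced.** Two steps are needed: recovery is summarised, and flagged values are dropped.

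- Within one child (illustration): one pre-inhibitor value of 1.6–2.0 and one confirmatory value near 0. With both kept, the mean is (1.6 + 0)/2 to (2.0 + 0)/2 = 0.8–1.0. With the flagged value dropped, it is 1.6–2.0.
- Across children (illustration): if a share f of the recoveries is 0 and the rest average R, the mean of all values is (1 − f) × R, and the mean after dropping is R. The ratio is 1/(1 − f): 1.05 for f = 0.05, 1.11 for f = 0.10, 1.33 for f = 0.25. The documents do not give f, so these show direction and scale and are not estimates.

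**Presentation.** Could the Supplement's wording mean no more than the presentation already set in section 4.7? That is unlikely. It adds a listing as a separate item, and the same section assigns surgical outcomes to a listing and the pharmacokinetic summary to the final report. Recovery is treated differently from both. The conflict with SAP v2.0 sections 2, 4.7 and 6.2.1 stands.

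**The case against.** The strongest reply is that harm needs two steps that SAP v2.0 does not state. It creates a flag but never says what the flag does, and the exclusion from tables is written only in the Part A SAP. Under SAP v2.0 alone, recoveries are listed, so low values stay visible. Dataset and table details sit in separate "documents which are an integral part of this SAP"; these were not available, and the derivation there may depend on inhibitor status. All of this stands, and it limits the consequence. It does not remove the defect: the rule as written labels real values not valid, and the later Supplement makes a summary a real prospect.

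Several stronger readings are tempting, but the documents do not support them:

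- A reader might infer that Part B expects inhibitors in up to half of the children. SAP v2.0 section 1 gives that figure as background on severe FVIII deficiency, not as a Part B assumption.
- A reader might multiply such an incidence by about 50 children to count the affected recoveries. The count would be too loose to use. SAP v2.0 says that few recoveries were collected and that children who develop an inhibitor should leave Part B. It covers Part B without the extension, and the final visit on discontinuation is only requested.
- A reader might seek a fixed threshold above which dropping values must raise the mean, such as 10/15 = 0.67 at 15 IU/kg. Protocol section 6.1.1 allows a 250 IU vial for initial treatment at any weight. At an assumed 20 kg that is 12.5 IU/kg, and the cut becomes 10/12.5 = 0.80. Only an expected direction can be claimed.
- A reader might infer that inhibitor incidence is understated. SAP v2.0 section 6.4.3 bases it on Bethesda titres, not on recovery.

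**Conclusion.** The point holds in this limited form. Two validity rules rest on a premise that fails for inhibitor-positive samples, and they are applied without that condition in a population where the protocol plans recovery sampling at inhibitor confirmation. Complete loss of recovery is always flagged. The 10 IU/dl rule flags values below roughly 10–42% of the expected rise, depending on dose, with a pre-infusion level near 0.

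The consequence depends on an unresolved conflict. If recovery is summarised and flagged values are dropped, the summary loses its lowest inhibitor-affected values and is expected to look too favourable, by an unknown amount. If recovery is only listed, the harm is a wrong label beside a visible value.

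The conclusion assumes dose proportionality from the 50 IU/kg figure and no overriding rule in the specification documents that were not available. The analysis is descriptive, and the primary bleed rate and inhibitor incidence are unaffected. It is worth correcting but does not threaten the main results.

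**What to change.** 1. Apply the pre ≥ post and 10 IU/dl rules only to samples without a positive inhibitor at that time, using the definition with confirmation in SAP v2.0 section 6.4.3. Show samples of unknown inhibitor status separately.
2. Date inhibitor status with the start and end variables in section 6.2.2. Extend them to high-titre children in Part B, because that table reserves both high-titre periods for the extension.
3. State in the SAP how flagged values are used, and reconcile sections 2, 4.7 and 6.2.1 with Supplement section 2.1.
4. If recovery is summarised, retain inhibitor-affected values, show them by inhibitor status at sampling, and report the number flagged under each rule.

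The pre > 40 IU/dl rule can stay as it is.

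The cost is SAP wording, derivation of the high-titre dates for Part B and, if a summary is produced, one table split. There are drawbacks. Inhibitor-positive groups will be small, and the overall mean may look less favourable. Swapped sample pairs in inhibitor-positive children would have to be caught by data queries. Low values before an inhibitor is detected would still be flagged, since routine testing has a gap between 20 and 50 exposure days. Some samples will have unknown status: children who start on demand have their first recovery when prophylaxis starts (protocol section 7.1.2.2), which need not coincide with an inhibitor test.

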6.4 Dosage and administration

The dose selections for this study are based on the recommended dosage for Kogenate® FS/Bayer.⁶ The study medication, BAY 81-8973, has been shown to have similar biological activity to Kogenate® FS/Bayer, which is currently approved in more than 50 countries for the treatment of hemophilia A.

In Part A of this study (as of Amd 1), subjects will receive prophylaxis treatment with BAY 81-8973 at least 2 times weekly with a dose of 25-50 IU/kg at the choice of the investigator and according to local standards and previous treatment. The dose *should be rounded to the appropriate vial size. In Part B, prophylaxis may be started with a low dose, once a week treatment schedule. The recommended dose is 15-50 IU/kg, (minimum 250 IU) (as of Amd 6). For all subjects, the (as of Amd 1)* frequency as well as the dose may be adapted to the individual needs up to daily if needed to accommodate for the subject's activities *or sports participation. (as of Amd 1)*

Any bleeding *events* occurring in subjects receiving prophylactic care will be treated according to the *local* standard of care and severity of the bleed. *(as of Amd 1)*

Subjects will be injected by parents/caregivers at home, *at a* facility near *the* subject's home, *homecare nurse (as of Amd 1)*, or by the investigator/delegate during the study visits. Children may also *self-infuse, if under the supervision of a responsible adult to ensure adherence to the prescribed treatment regimen. (as of Amd 1)*

For the optional PK study, each subject will receive *an exact* dose of 50 IU/kg of BAY 81-8973. The dose will be prepared by a pharmacist or nurse at the study *site*. This dose *is* expected to increase the plasma level of FVIII to approximately 80-100% FVIII activity. *(as of Amd 1)*

During surgery (both major and minor) dosing with BAY 81-8973 will follow the same standard practice as followed for Kogenate® FS/Bayer (Appendix 14.1). The guidelines are designed to maintain adequate hemostatic FVIII levels and provide instructions based upon the type of surgical procedure to be undertaken. *(some text deleted as of Amd 1)*

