7.3.2 Efficacy procedures

7.3.2.1 Incremental recovery of Factor VIII (as of Amd 1)

Samples for FVIII trough levels will be collected in the *clinic* before the next planned *prophylactic infusion* as scheduled. Recoveries should be performed in conjunction with planned prophylaxis *infusions, using the subject's usual dose (exception, during optional PK). Infusions given at study visits will not be recorded in the EPD, but in the site patient records, which will be the source document and will be used to enter this information in the CRF. (as of Amd 1)*

Levels of *BAY 81-8973* will be determined in a central laboratory with the chromogenic *method. (as of Amd 1)*

FVIII trough levels will be determined in the blood samples collected before the *scheduled BAY 81-8973 infusions* at Baseline, Month 1, Month 2, and Month 6 (or final visit) *in Part A; or at Baseline, ED 20, and final visit (ED 50) in Part B.* The measurement should be performed *at least 48 h after last infusion of BAY 81-8973. (as of Amd 1)*

Incremental recovery at 20-30 min after end of *infusions (as of Amd 1)* will be determined at Baseline, Month 1, 2, Month 6 (or final visit), *1st extension visit and final extension visit (as of Amd 6).* Incremental recovery should only be measured when the subject is not actively bleeding. The exact sampling times before and after *infusion (as of Amd 1)* have to be documented in the CRF.

A determination of recovery should also be performed with the confirmatory inhibitor test (as of Amd 7).

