6.2 Efficacy

All subjects receiving study drug who have infusion/bleeding data from the EPD will be included in the efficacy analysis. The primary efficacy variables will be the annualized number of total bleeds (sum of spontaneous bleeds, trauma bleeds, and untreated bleeds) that occur within 48 hours after all prophylaxis infusions. Also summarized will be annualized number of joint bleeds, spontaneous bleeds, and trauma bleeds that occur within 48 hours after all prophylaxis infusions. Additional variables summarized will be annualized number of total bleeds, joint bleeds, spontaneous bleeds, and trauma bleeds. Other variables summarized will be the number of treatments required to control all bleeds and the subject's assessment of the response to treatment of all bleeds (poor, moderate, good, or excellent).

All efficacy variables will be summarized using the ITT analysis set. The primary efficacy variable will also be summarized using the PPS.

For subjects undergoing surgery (both major and minor), FVIII levels from the day prior to surgery through the post-operative period will be summarized by timepoint and listed. Study drug and blood product infusions will also be summarized and listed for these subjects, as well as blood loss at surgery and the assessment of hemostasis during the perioperative period by both the surgeon and the investigator.

Factor VIII concentration values and recovery values will be summarized by time point.

recovery = (post-infusion FVIII – pre-infusion FVIII) * weight / dose (in IU)

If a Factor VIII concentration value is below the LLOQ (lower limit of quantification), a data point will be substituted by one half of this limit.

A validity flag for recovery values and their corresponding pre- and post-infusion FVIII values will be created. These values will be considered valid except when any of the following conditions apply:

- If pre-infusion FVIII >= post-infusion FVIII [biologically impossible in the absence of inhibitors]
- If pre-infusion FVIII > 40 IU/dl (note 1 IU/dl=1%) [protocol violation]

In the tables displaying descriptive statistics of recovery values, if a recovery is flagged as not valid, then the corresponding pre-infusion FVIII, post-infusion FVIII, and recovery values will not be included.

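### Part B SAP 4.7 picks duplicate FVIII records by highest value and judges validity by value instead of recorded sampling time; its 40 IU/dl limit, shared with Part A, misses most failed 48-h washouts

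*SAP*

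**What the plan says.** **Part B SAP (version 2.0), 4.7 Recovery.** Recovery is defined as "Recovery=(post-infusion FVIII value – pre-infusion FVIII value) * body weight / dose (in IU"). The section says exact sampling times and the dose will be documented. On duplicates it states that "if there are multiple FVIII values for a subject and timepoint, only the record with the highest FVIII will be used", and "The others values will be excluded from the analysis dataset". A record is invalid only if the pre-infusion value is at or above the post-infusion value, or under two limits: "If pre-infusion FVIII > 40 IU/dl (note 1 IU/dl=1%) [protocol violation"] and "If post-infusion FVIII < 10 IU/dl (note 1 IU/dl=1"%). No condition uses time.

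**Part A SAP, 6.2 Efficacy.** "These values will be considered valid except when any of the following conditions apply": pre-infusion at or above post-infusion, and the same 40 IU/dl limit. There is no highest-value rule. FVIII and recovery are summarized by time point. The last trough, separately, is grouped by hours since the previous infusion.

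**Protocol.** Section 7.3.2.1 sets the pre-infusion sample "at least 48 h after last infusion of BAY 81-8973", the recovery sample at 20-30 min after the end of infusion, and has exact times recorded. Section 6.4 states that 50 IU/kg is "expected to increase the plasma level of FVIII to approximately 80-100% FVIII activity".

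**Part B reporting.** SAP 4.7 and 6.2.1 provide listings only for these values. Supplement 1.0, section 2.1, names recovery a secondary parameter and has it summarized under 4.7.

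**The concern.** Recovery and pre-infusion level are defined by when the sample was taken. Selecting or validating records by the value itself lets the outcome decide which data count. If a low post-infusion result is repeated, the rule deletes the low one. A limit labelled as a protocol-violation check also gives false assurance if it cannot see the violation.

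Recovery is a secondary objective, and protocol 7.3.1 calls it the main surrogate efficacy parameter. Low values are informative here: recovery accompanies the confirmatory inhibitor test (7.3.2.1), and a decreased recovery is part of the definition of a clinically relevant inhibitor (6.1.5).

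**Working it through.** **Inputs from the documents.** 50 IU/kg gives 80-100 IU/dl, so the rise is 80/50 = 1.6 to 100/50 = 2.0 IU/dl per IU/kg. Prophylaxis doses are 25-50 IU/kg (Part A) and 15-50 IU/kg (Part B). The washout is at least 48 h. The 40 IU/dl limit comes without a derivation, so there is nothing to reproduce.

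**Assumptions.** First-order decay. Half-life 6-14 h; the documents give only a floor of 6 h, as an ITI success criterion (6.1.5). Assay CV 5-20%. The numbers of duplicates and mistimed samples are unknown.

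**1. What the 40 IU/dl limit can detect.** Peak = dose x 1.6 to 2.0. Time until the level falls to 40 = half-life x log2(peak/40). The last column is the level 24 h after a single dose.

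| Dose (IU/kg) | Peak (IU/dl) | Above 40 for | Level at 24 h |
|---|---|---|---|
| 15 | 24-30 | never | 1.5-9.1 |
| 25 | 40-50 | 0-4.5 h | 2.5-15.2 |
| 50 | 80-100 | 6.0-18.5 h | 5.0-30.5 |

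Every single-dose 24-h sample passes. Even daily 50 IU/kg gives a 24-h level of 5.3-43.8, above 40 only at the extreme. To read 40 at 48 h after a peak of 100, the half-life would have to be 48 / log2(100/40) = 36 h. A compliant 48-h sample is expected at no more than 9.3 IU/dl (50 IU/kg, 2.0, half-life 14 h).

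**2. Effect of a missed washout.**
- Pre-infusion level, 24 h against 48 h: ratio = 2^(24/half-life) = 3.3 (14 h) to 16 (6 h).
- Recovery: the residual is subtracted, so only its decay between the two samples remains. With samples 0.5 h apart and the same dose given before, the relative change is 2^(-t/half-life) x (2^(-0.5/half-life) - 1). At t = 24 h and half-life 12 h this is 0.25 x (0.9715 - 1) = -0.71%. The range is -0.35% to -0.75% at 24 h and about -1.4% at 12 h.

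**3. Highest of several replicates.** The expected maximum of two normal values lies 0.564 SD above the mean; of three, 0.846 SD.
- Post-infusion, two replicates: 0.564 x CV = +2.8%, +5.6%, +8.5% and +11.3% at CV 5, 10, 15 and 20%. Three replicates at CV 10%: +8.5%.
- Pre-infusion, two replicates at 6.25 IU/dl (half-life 12 h, 48 h after a peak of 100), CV 10%: 0.564 x 0.10 x 6.25 = +0.35 IU/dl on the level, which lowers a recovery based on a rise of 100 by 0.35%. The pull is larger if the duplicates were drawn at different times.

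These are shifts per duplicated timepoint. If, for illustration, 5% of timepoints had two post-infusion replicates, the mean would move by 0.05 x 5.6% = 0.28%.

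**4. Late post-infusion sample.** With a low pre-infusion level, loss against 25 min (0.42 h) = 1 - 2^(-(t - 0.42)/half-life). For half-life 8-14 h this is 3-5% at 1 h, 8-13% at 2 h and 16-27% at 4 h (34% at 4 h if the half-life is 6 h). None of the conditions is built to detect this.

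**The case against.** **Recovery is largely protected from missed washouts.** A reader might infer that the 40 IU/dl limit leaves recovery materially biased. It does not: subtracting the pre-infusion level reduces the effect to under about 1.5%. This stands.

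**The highest-value rule need not inflate recovery overall.** A reader might infer a uniform upward bias. The documents do not support that. The rule is in Part B only, it lowers recovery for pre-infusion duplicates, and where post-infusion records differ in time the highest is normally the earliest, often the one nearest 20-30 min. The upward bias is clear only for true replicates. This stands, but recorded time would make the same choice without favouring high values.

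**Part A already handles troughs by time.** Its last-trough bands and correlations use hours since the previous infusion, so a 24-h sample enters neither. This stands. In Part A the problem is confined to the by-timepoint FVIII and recovery summaries.

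**Part B exposure may be small.** SAP 2.0 expects few values and only lists them, and most Part B subjects are expected to start once weekly (protocol 7.1.2), which makes missed washouts less likely. This stands in part: Supplement 1.0 has recovery summarized under 4.7, and SAP section 2 defers the recovery objective to the final analysis.

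**Other controls exist.** The protocol fixes the timing, the per-protocol set is primary for Part A recovery (SAP amendment of 18 July 2013), and both SAPs plan a review of validity and refer to dataset specifications not available here. Timing may be handled there. The written rules in 4.7 still direct the programmer to select by value.

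**Conclusion.** The point holds for the rules as written. Part B 4.7 selects duplicates by outcome and ignores recorded times, and the 40 IU/dl limit in both SAPs cannot detect most missed 48-h washouts. The second conclusion does not change at any half-life from 6 to 14 h.

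The consequences differ by measure. Pre-infusion FVIII is overstated when a washout is missed. Recovery is affected by replicate selection (net sign not fixed) and is lowered by late post-infusion samples. The sizes rest on the assumed half-life and CV, and the effect on any reported mean depends on counts that the documents do not give. They therefore do not support a claim that reported recoveries are wrong by a particular amount.

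The primary bleed endpoint and the BU-based inhibitor definition in Part B SAP 6.4.3 are untouched. The change should be made, but it does not threaten the trial's main conclusion.

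**What to change.** In Part B SAP 4.7:
- Choose among multiple records by recorded time: the post-infusion record closest to 20-30 min after the end of infusion, and the last pre-infusion record. Average true replicates.
- Flag validity by recorded time since the last FVIII dose (at least 48 h with a stated tolerance, for example the 6 h margin of the Part A SAP's 48-h trough band) and by a stated post-infusion sampling window.
- List every excluded value, with its time and the reason.

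Apply this to recovery in the Part B and final reports. Part A's 6-month analysis is already reported, so a sensitivity summary is enough there. Reconcile the listing-only statements in SAP 2.0 (4.7 and 6.2.1) with Supplement 1.0, section 2.1, which has recovery summarized.

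The cost is SAP wording and programming, plus one sensitivity table for Part A. The sampling times are already collected. The downside is that a few mistimed recoveries leave the summary.
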